**PROTOCOL AMENDMENT SUMMARY OF CHANGES TABLE**

| DOCUMENT HISTORY  |             |
|-------------------|-------------|
| Document          | Date        |
| Amendment 2       | 17-JUN-2021 |
| Amendment 1       | 19-JUN-2019 |
| Original Protocol | 18-OCT-2018 |

**Amendment 2- 17-JUN-2021****Overall Rationale for Amendment 2:**

This protocol amendment was created to make some minor changes to the study design, add clarity to some sections of the protocol, and to correct typographical errors and inconsistencies. Protocol changes are described in the table below.

| Section # and Name                      | Description of Change   | Brief Rationale  |
|---|---|--|
| Title page                              | Authors list removed  | Updated based on template instructions   |
| INVESTIGATOR PROTOCOL AGREEMENT PAGE    | Added the investigator protocol agreement page  | To meet GSK SOP requirement  |
| Section 1. Synopsis                     | Updated information related to overall design and number of participants  | Align the synopsis with the update of the study design in Section 5 of this protocol   |
| Section 2. SCHEDULE of ACTIVITIES (SoA) | Added a clear definition of a month as 30 days and also adjusted the visit window from 28 days to 30 days for V2, V3 and V4   | To ensure consistency in study operation   |
|   | Clarified that for the 4 clinic visits (V1-V4), all the participants should be clinically stable with no exacerbation or other acute medical event for at least 30 days prior to each scheduled visit | Ensure that the schedule visits intend to assess participants in stable state to avoid misunderstanding  |
|   | Edited the timeframe around the 2 exacerbation visits to “at least 21 days” instead of “at least 6 months”  | To prevent this study from missing the exacerbations that occurred within 6 months of each other or at the start of study  |
|   | Added a statement for the sub-cohort that the planned clinic visits should be scheduled with an interval of at least 60 days after a completed exacerbation visit                                     | To provide an appropriate time interval between an exacerbation visit and a scheduled visit for stable state   |
|   | Edited the visit window of Visit 1 to “+7 days” instead of “+3 days”  | To ensure that all baseline procedures can be completed within a more reasonable window once there is any participant who is been required to undergo a nucleic acid test of COVID-19 before initiating the onsite screening procedures. |

|  |   |  |
|--|---|--|
|  | 
Updated the footnote 6 to the procedure of lung HRCT scan to ensure “The CT scan for an exacerbation visit should only be performed if the last study CT scan performed was more than 14 days.”
 
Added a footnote to the procedure of blood draw and sputum respectively to ensure “No systemic corticosteroids or antibiotics used within 14 days before collecting the blood or sputum samples
 
Added a sputum sample point at V2 for those who do not have a qualified sputum cytology sample at baseline (footnote 11)
 | 
To clarify the minimal time interval between the CT scan for an exacerbation visit and a CT scan for a scheduled study visit
 
To ensure obtain accurate sputum and EOS assessment data in COMPASS study. Any use of systemic corticosteroids or antibiotics within 14 days may affect their results
 
Provide another chance to ensure the collection of sputum cytology samples in this study
 |
| Section 3.1.
Benefit/Risk
Assessment | Updated the risk assessment related to ionising radiation and specified that participants <50 years of age will not be included in the sub-cohort, nor will females of child bearing potential  | To make information clearer  |
| Section 5.1.
Overall Design             | Added study sites in Xiamen and the rationale behind it   | Xiamen, another coastal city of southeast China, is near Guangdong province. We added one site (maybe more if needed) in Xiamen based on feasibility to enhance the enrolment of this study  |
| Section 5.2.
Number of
Participants  | 
Removed the minimum requirement (15%) for the proportion of never smokers in each group of main cohort while retained the maximum requirement (30%), and updated Figure 2
 
Added flexibility for recruitment targets of GOLD I and GOLD II in main cohort
  | 
To add the flexibility for Never-smoker subgroups based on the feasibility considerations
 
To ensure a wide and even distribution of airflow limitation across the patients recruited to this study
   |

|   |  |  |
|---|--|--|
|   | 
Added flexibility for the target number of never smokers in each group of sub-cohort and updated figure 3
 
Added flexibility for recruitment approach of GOLD III never smokers in sub-cohort
 
Adjusted the definition of Exacerbator. An exacerbation in the previous year is defined by the occurrence of an episode of increased cough (with or without phlegm), shortness of breath or chest symptoms (chest discomfort or tightness) which lasted 48 hours or more and interfered with the Participants usual activities. The requirement for treatment with antibiotic ± oral corticosteroid has been removed
 | 
To add the flexibility for Never-smoker subgroups based on the feasibility considerations
 
To ensure that the target of enrolment of 50 patients with GOLD III was achieved as planned
 
COMPASS is primarily designed to study patients with mild-moderate airways disease. Such patients have fewer treated exacerbations than those with more severe airflow limitation. This does not mean that they do not have exacerbations, it's equally possible that they may be less likely to report them. Studies with the EXACT diary have shown that there may be 2-5 more unreported exacerbations than those that are reported (Jones, 2014; Betsuyaku, 2018). Patients with unreported exacerbations appear to be less symptomatic when they are stable than those who do report them (Leidy, 2014). To ensure that we can identify and recruit patients whose exacerbations are not troublesome enough to make them seek treatment, we will use an exacerbation definition based on a definition used in two population surveys (BOLD and CANCOLD) that included mild subjects (Buist, 2007; Tan, 2014)
 |
| Section 6.1.
Inclusion
Criteria-COPD,
Chronic
Bronchitis and
healthy
participants | Changed the age limit for all main cohort participants from 50 years to 40 years   | To involve in participants aged 40-50 to enable the recruitment of more early-stage COPD and keep consistent with other large COPD epidemiological studies   |

|   |  |   |
|---|--|---|
| (common to all the group of participants)   | Identified the additional criteria for each group in the sub-cohort to allow participants aged 50-80 years   | Provide clear criteria for the sub-cohort to avoid misunderstanding   |
| Section 6.1. Inclusion Criteria-COPD, Chronic Bronchitis  | Reduced the pack-year limit for all ever smokers in the main cohort from 10 to 1   | Allow the recruitment of ever smokers with 1-10 pack-year in the main cohort. Pack years smoking is very closely related to age. The typical patient with established moderate-severe COPD who is for example 65 years old will have smoked for 20 years more than a 45 year old.   |
| Section 6.1. Inclusion Criteria-COPD participants   | Edited “A baseline (post-bronchodilator) FEV1/FVC ratio <70%” to “A baseline (post-bronchodilator) FEV1/FVC ratio <0.70”

Removed the requirement for the severity of historical exacerbation event (moderate or severe) in the additional criteria for sub-cohort | Use a fraction to 2 decimal places rather than a percentage of a whole number to make this inclusion criterion more precise and keep consistent with other COPD studies. This becomes especially important for patients with mild airflow limitation – who are an important subgroup in COMPASS

Ensure consistency across the protocol |
| Section 6.1. Inclusion Criteria-Chronic Bronchitis and healthy participants   | Edited “Baseline post-bronchodilator FEV1/FVC ratio >70%” to “Baseline post-bronchodilator FEV1/FVC ratio ≥0.70”   | To involve in participants whose Baseline post-bronchodilator FEV1/FVC ratio is greater than or equal to 0.70   |
| Section 6.2. Exclusion Criteria-COPD, Chronic Bronchitis and healthy participants (common to all the group of participants) | Specified that COVID-19 should be excluded in each group

Removed “Mandarin” in the No. 13 exclusion criterion related to read and understand Chinese  | Provide specified information

To make it clear. There are lots of local languages in China. Mandarin is the most widely used official language. To allow the participants to participate in the study who can speak other local languages except Mandarin  |

|  |  |   |
|--|--|---|
| Section 6.2.
Exclusion
Criteria-Chronic
Bronchitis and
healthy
participants | Edited “FVC<80% Predicted”
to “Post-bronchodilator
FVC<80% Predicted normal”   | According to GOLD and
ATS/ERS criteria, clarify the
requirement of post
bronchodilator FVC <80%
Predicted normal.   |
| Section 6.4.
Screen Failures  | Added “Only in certain special
cases, re-screening of
participants will be allowed.
Investigator will be asked to
provide detailed information.
Special cases will be discussed
at the EST (Empowered Study
Team) meeting. After
permission from the medical
monitor of this study is granted,
the participants can only be re-
screened once.”               | Re-screening was allowed for
certain special cases to prevent
missing early stage COPD
participants, especially the
GOLD 1 COPD participants  |
| Section 9.1.
Baseline data
collection  | Added the item of “Number of
exacerbations in the previous 12
months and 24 months”

Added more airway parameters
for spirometry  | Ensure consistency across the
protocol

To achieve a more
comprehensive evaluation of
small airway function – which
is particularly important in mild
and early disease  |
| Section 9.2.3.
Spirometry   | Specified the same
measurements as baseline
spirometry

Removed the requirement of
“Spirometry will be performed
after the completion of any
PRO questionnaires”  | Ensure consistency across the
protocol

To reduce the visit time of
participants  |
| Section 9.2.6.
Patient Reported
Outcome
Measures                                  | Added “All Patient reported
outcome measures should be
collected in a nice, quiet setting
without distractions (e.g.,
television, cell phones).”

Removed the original timing
and order requirements for
collecting the CAT, mMRC and
SGRQ-C assessments. Only
required to collect CAT at the
beginning of the study visits
(before any other procedures). | To ensure the data quality, the
most important is to have a
nice, quiet setting to do the
assessments.

To minimize the visit duration
of the study participants. It’s
not necessary to require the
CAT, mMRC and SGRQ-C
assessments to be done in a
fixed order at the beginning of
the study visits. |

|  |   |  |
|--|---|--|
| Section 9.2.6.2.
Evening Diary
(sub-cohort only)             | Removed the level 5 headings and presented headings in bullets. 

Exacerbations of Chronic Pulmonary Disease Tool (EXACT) and Evaluating Respiratory Symptoms in COPD (E-RS: COPD)

Additional questions

 | Updated as per template requirements                                     |
| Section 9.3.
Exacerbation Visits (sub-cohort only)              | Updated figure 4: removed X in second box and corrected spelling of units, as well as reflected use of EXACT score  | To correct the typo  |
| Section 10.2.8.
Interim Analyses                                | Deleted the statement of “Scientific steering committee will oversee the interim analyses”. Add the statement, The Scientific Steering Committee will have sight of, and approve, all requests for analyses that come from the Working Groups                 | Clarify the responsibilities of the Scientific Steering Committee        |
| Section 11:
References  | Added references: Jones, 2014; Betsuvaku, 2018; Leidy, 2014; Buist 2007; Tan, 2014  | To support the data  |
| Section 12.3.
Appendix 3:
Contraceptive and Barrier Guidance | Added this guidance   | Provided the information related to Woman of non-child bearing potential |
| Throughout   | Corrected spelling errors, added abbreviations to abbreviation list, added punctuations wherever applicable   | For consistency and clarity  |

## 1. SYNOPSIS

**Protocol Title:** Investigation of the Clinical, Radiological and Biological factors associated with disease progression, phenotypes and endotypes of COPD in China

**Short Title:** Investigation of COPD disease phenotypes and endotypes in China

**Rationale:**

Chronic Obstructive Pulmonary Disease (COPD) is a leading cause of morbidity and mortality resulting in significant humanistic and economic burden to patients, healthcare system and society worldwide. COPD prevalence in China has been significantly increasing. A national screening survey, conducted in 2002-2004, reported that the overall prevalence of spirometry-defined COPD among people over 40-year-old was 8.2% in China. The recently published China Pulmonary Health study (2018) indicated the prevalence of COPD among Chinese over 40 years old had increased to 13.7%. A study in 2013 including 634 COPD patients from 83 tertiary hospitals in 17 provinces in China estimated the average cost of COPD per patient per year to be RMB 20,107.58. Further, COPD led to a large productivity loss of RMB 6,941.33 yuan/per person-year; the value of working time loss was RMB 613.86 yuan/per person-year. Although COPD management in China has been greatly improved over the past decades, many challenges persist. One of them is substantial under-diagnosis: up to 65% of people with airflow limitation pattern compatible with COPD were found not to have a clinical COPD diagnosis. Further, majority of COPD patients (64.7%) exhibit high symptom burden, defined as at least one respiratory symptom (cough, phlegm, wheezing, and breathlessness), despite treatment.

COPD prevalence and disease burden have been well studied in North America and Western Europe through large cohort studies. The ECLIPSE study recruited patients with moderate-severe airflow limitation from secondary care; COPDGene, COPDMAP and SPIROMICS largely recruited patients of a wide range of disease severity from a variety of healthcare settings. However, so far there have been no dedicated cohort studies conducted in China with a specific focus on high density phenotyping of COPD, including biomarkers and clinical features associated with disease activity, severity and progression in China. Existing large populational cohorts, like the China Kadoorie Biobank, inform on the extent of disease burden of airflow limitation; however, due to its general population-based nature, they provide only limited information on clinical and humanistic burden and therapeutic management of diagnosed COPD.

With an aging population and persistent air pollution in China, the humanistic and economic burden of COPD is expected to increase and will require more healthcare resources in the future. COPD has been identified as a key disease of focus under the China government's Thirteenth Five programme. Therefore, to inform clinical practice and aid public health resource allocation, it is important to advance knowledge and understanding of disease progression and clinical management of COPD, especially at early disease stages, in China.

Whilst COPD is a common disease across the world, its phenotypes and patterns of disease progression may differ geographically, impacting approaches to precision

medicine in China. Recent international studies showed substantial geographic variations in respiratory symptoms and other respiratory illnesses in COPD patients. The disease progression of COPD and clinical management in China is largely unknown. Recent studies in non-Asians have demonstrated that acute exacerbations of COPD (AECOPD) can be subdivided by type: infections (bacterial and/or viral), eosinophilic, and pauci-inflammatory and each subtype has been associated with increased levels of specific blood biomarkers. Moreover, recent data indicate that bacterial and eosinophilic exacerbations are likely to repeat within an individual, suggesting endotypic differences in Western frequent exacerbators. There is a need to compare and validate findings from cohorts conducted in predominantly Caucasian populations to guide clinical development of new COPD medicines in China.

With recent technology advances, Electronic Data Capture (EDC) has steadily increased in clinical research. Meanwhile, the Electronic Health Record (EHR) systems are becoming essential to routine clinical practice and has the potential to facilitate large-scale clinical research. Therefore, this study also aims to assess the feasibility of integrating EHR, electronic clinical outcome assessments (eCOA), biomarkers and physical activity data to support application of Digital Data Analytics (DDA) platform in China (e.g. direct digital data capture and integration).

### Objectives and Endpoints:

| Research Questions & Objectives  | Endpoints  |
|--|--|
| 
1. Evaluate whether the predictors of COPD disease progression identified in Western cohorts are applicable in China.
 
 
• To evaluate disease progression in COPD and non-COPD participants over 2.5 years as assessed by lung function, exacerbation frequency, health status, lung high-resolution computed tomography (HRCT) scan, and changes in physical activity.
 
 | 
Main cohort
 
Change from baseline in forced expiratory volume in 1 second (FEV1) and rate of decline in FEV1
 
Change from baseline in forced vital capacity (FVC) and rate of decline in FVC
 
Rate of moderate/severe exacerbations*
 
Change from baseline in COPD Assessment Test (CAT) score
 
Assess CAPTURE to identify undiagnosed COPD patients in Chinese population
 
Frequency of Clinically Important Deterioration (CID) and its components
 
Death
 
Additional for sub-cohort
 
Change in Evaluating Respiratory Symptoms in COPD (E-RS: COPD) scores
 |

| Research Questions & Objectives  | Endpoints   |
|--|---|
|  | 
Characterisation of EXAcerbation of COPD Tool (EXACT) events
 
Change from baseline in airway thickness by lung HRCT
 
Change in lung density by lung HRCT
 
Change in physical activity measures (e.g. Daily steps, bouts of activity per day)
   |
| 
2. Characterise stable disease and exacerbation phenotypes in China through assessment of blood biomarkers, lung microbiome and radiological features of COPD
 | 
Main cohort:
 
Plasma fibrinogen and high-sensitivity C-Reactive Protein (hsCRP)
 
Differential blood cell count (e.g. eosinophils, neutrophils) and haemoglobin
 
Additional for sub-cohort
 
Blood biomarkers including but not limited to Serum interferon- <math>\gamma</math> -inducible protein -10 (IP-10), soluble Receptor for Advanced Glycation End Products (sRAGE), Club cell protein (CC16) and HbA1c
 
Sputum microbiome as assessed by molecular methods
 
Sputum total differential cell counts percentage CCI
 
███████████
 |
| 
3. Characterise treatment pathways and healthcare resource utilization and costs in COPD
  | 
Frequency of treatment with COPD medications; Treatment patterns at the time of study entry and during the study period
 
Count of outpatient visits, emergency visits, hospitalizations (overall and COPD-specific)
 
Direct medical costs associated with COPD medications and COPD disease management
 
Insurance coverage and patient out-of-pocket payment
   |

| Research Questions & Objectives  | Endpoints |
|--|-----------|
| 
4. Test the feasibility of integrating electronic health records, electronic clinical outcome assessments (eCOA) and physical activity data to support application of digital data analytics (DDA) platform in China studies (e.g. direct digital data capture and integration)
 | NA        |

\*Moderate exacerbations are defined as COPD exacerbations that require either systemic corticosteroids (intramuscular (IM), intravenous, or oral) and/or antibiotics. Severe exacerbations are defined as COPD exacerbations requiring hospitalization (including intubation and admittance to an ICU) or result in death.

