### **Number of Participants:**

A total of 2,000 participants are planned to be enrolled, consisting of 1,700 participants with COPD, 180 with chronic bronchitis but without COPD (i.e. without fixed airflow limitation), and 120 never smoker non-COPD healthy controls. COPD subjects will be further classified using the GOLD grades I – IV (i.e. mild, moderate, severe and very severe airflow limitation). To better understand the disease progression of early-stage COPD, i.e. GOLD I and II grades, targets will be set for COPD participants will be recruited in the following manner: GOLD I: 700, GOLD II: 700, GOLD III: 200, GOLD IV: 100. The purpose is to ensure a wide and even spread of the degree of airflow limitation across the study population. The number of participants recruited to each GOLD grade will be monitored and targets adjusted as necessary to ensure an even distribution. Among each GOLD grade and chronic bronchitis group, up to 30% of never smokers will be recruited in each group. All patient population sizes are approximate and allow  $\pm 10\%$  for feasibility.

All participants will be recruited from Type A and Type B hospitals in Guangdong and Fujian province. To represent the difference in patient profile and practice between different hospitals, the ratio of participants from Type A and Type B hospitals will be 2:1. Specifically, healthy control participants will be recruited from the physical examination department at site hospitals. For the healthy control group to be comparable with COPD participants, pre-set criteria on demographic profile (i.e. age, gender) will be specified in detail in the SRM based on previous studies or available real-world data. When appropriate, matching methods will also be used to adjust for differences in baseline factors (e.g. age, gender) in statistical analyses. Matching of the cohorts will be considered to address specific questions, e.g. biomarkers analysis. Methods to achieve balanced cohorts will be chosen based on a hypothesis and the extent of underlying differences between the cohorts and detailed in the main or ad-hoc RAP.

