This study will also set up a Biomarker and Digital sub-cohort aiming to identify early disease and rapid progression and associated endotypes among Chinese COPD patients through enhanced repeated collection and analysis of biological samples and chest computer tomography. COPD is characterised by abnormal spirometric results, with a focus on FEV1. Decline in FEV1 is currently the gold standard for assessment of COPD progression. However, disease burden and worsening are also inextricably linked with disease activity represented by symptom load and exacerbations of COPD. This study

will aim to evaluate multifactorial framework of disease severity in Chinese population similar to work by Agusti and colleagues [[Agusti](#), 2016].

The selected 2.5-year follow up is required as a minimum period to achieve sufficient precision on the rate of decline in key study measures balanced against any perceived burden this study may impose on participants which could result in early withdrawal from the study.

The clinical, radiological and biological factors identified to be associated with disease progression in Western cohorts will be investigated to test the hypotheses whether these predictors are applicable in China and characterise the exacerbator phenotype in China. Healthcare resource utilization and costs in COPD will be assessed to evaluate the economic impact of COPD for the different groups of COPD patients in Guangdong province. The following table lists all study endpoints and summarizes the rationale of including them.

| Study Outcomes  | Rationale   |
|---|---|
| 
 
Change from baseline and rate of decline in FEV1 and FVC
 
   | 
 
Change in FEV1 is currently the gold standard for assessment of COPD progression.
 
  |

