### **2.2.2. Additional information for other endpoints**

Treatment pattern will be analysed in baseline (up to 90 days prior baseline to baseline), 0-6m, 6-18m and 18-30m.

HRU data will be analysed in total and by season, as defined in [14.2](#) .

Unless otherwise specified, the other endpoints will be analysed by visits.

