## 4. ANALYSIS POPULATIONS

**Table 2. Summary of Study Populations**

Population	Definition / Criteria	Analyses Evaluated
All Screened	
The All Screened Population will consist of all participants who sign the ICF to participate in the clinical trial.
 
Participants in this population will be used for screen failure summary.
	
 
• Study Population
 

Full	The Full Population will consist of all subjects (except subject PPD ) who are enrolled in the study and attend Visit 1, and not withdraw informed consent.	
 
• Study Population
 
• Disease Progression Analyses
 
• Phenotypic Analyses
 
• Treatment Pattern and Healthcare Resource Utilization/Cost
 
• Safety Analyses
 

Sub-cohort	Sub-cohort is a subset of Full population. Subjects who are enrolled in the Biomarker & Digital sub-cohort and who provided at least one additional sub-cohort assessment.	
 
• Study Population
 
• Disease Progression Analyses
 
• Phenotypic Analyses
 
• Treatment Pattern and Healthcare Resource Utilization/Cost
 
• HRCT analysis
 

HRU	HRU is a subset of Full population. The following sites are not feasible to capture data by HIS, thus the patients enrolled from the following sites will be excluded from HRU analysis: 238160, 238222, 237965, 237971, 238155.	
 
• Treatment Pattern and Healthcare Resource Utilization/Cost
 

[figure not shown]
\*: Subject PPD cannot be categorized into either of the study arms (COPD patients, Chronic Bronchitis patients or Healthy Control), thus excluded from the Full population.

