### **Endpoint: Number of Visits**

A descriptive summary of patient visits (Total, outpatient visits, emergency visits, and hospitalization) during the entire study period will be provided, both COPD related and non-COPD related visits will be presented.

A summary by season for COPD-related visits will also be provided, the definition of season is:

- Spring (Mar, Apr, May)
- Summer (Jun, Jul, Aug)
- Autumn (Sep, Oct, Nov)
- Winter (Dec, Jan, Feb)

The total follow-up period (year) and a summary of crude rate of COPD related and non-COPD related visits and the subcategory visits will be provided in a same table. The total follow-up and crude rate are defined as:

$$Total\ Followup\ Time = \sum (Last\ Visit\ Date - First\ Visit\ Date + 1)$$

$$Crude\ Rate = \frac{Sum\ of\ Number\ of\ Visits}{Total\ Followup\ Time\ (year)}$$

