## 9.2. Health resource utilization

**Table 6.** Overview of the Health Resource Utilization

Endpoint / Parameter / Display Type	Data Displays Generated		
	Table	Figure	Listing
Health Resource Utilization			
Number of outpatient visits	Y		Y
Number of emergency visits	Y		Y
Number of hospitalizations, length of stay	Y		Y
Treatment of exacerbation	Y		Y
Cost			
Total medical cost	Y		Y
Pharmacy cost	Y		Y
Other cost	Y		Y
Outpatient cost	Y		Y
Emergency cost	Y		Y

Endpoint / Parameter / Display Type	Data Displays Generated		
	Table	Figure	Listing
Hospitalization cost	Y		Y
Exacerbation cost	Y		Y

Summaries of healthcare resource utilization/cost will be provided at visit 2, 3, 4 for main cohort population and sub-cohort population. Subgroup analyses will include GOLD I-IV patients, chronic bronchitis patients and healthy control participants. Descriptive analyses will be calculated and tabulated by the abovementioned subgroups, using frequency and percentage for categorical variables and mean and standard deviation for continues variables, for healthcare resource utilization during the study. Stratified analysis will be performed according to COPD and non-COPD patients.

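### SAP 14.2 plans healthcare visits and COPD costs overall and by season, in a population that includes non-COPD arms and with no breakdown by arm or GOLD grade, so as written it does not deliver objective 3 or protocol 5.4

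*Protocol*

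**What the plan says.** Objective 3 (protocol Synopsis and section 4) is to "Characterise treatment pathways and healthcare resource utilization and costs in COPD". Protocol 5.4 gives the purpose of the utilisation and cost data: "to evaluate the economic impact of COPD for the different groups of COPD patients". Protocol 10.2.5 promises only suitable descriptive statistics for utilisation and cost, with no breakdown.

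The protocol plans 2,000 participants: 1,700 with COPD, 180 with chronic bronchitis and 120 healthy controls, with a ±10% tolerance on group sizes. The COPD arm is filled to targets: "GOLD I: 700, GOLD II: 700, GOLD III: 200, GOLD IV: 100". Section 5.2 allows the GOLD I and II targets to be adjusted during recruitment.

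SAP 2.2.2 says: "HRU data will be analysed in total and by season". SAP 14.2 then specifies:

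- for visits, "A descriptive summary of patient visits (Total, outpatient visits, emergency visits, and hospitalization) during the entire study period will be provided", with COPD-related and other visits shown, a seasonal table for COPD-related visits, and crude rates;
- for costs, an overall summary of COPD-associated direct medical cost, its components and payer split, and total cost by season.

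On the population, SAP Table 2 says: "HRU is a subset of Full population". It removes participants from five sites where the hospital information system (HIS) could not be used, and nobody on grounds of arm.

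RAP amendment 2, bound in the same file, was more specific. Its section 9.2 planned summaries by GOLD I-IV, chronic bronchitis and healthy control, and added: "Stratified analysis will be performed according to COPD and non-COPD patients". The version history records that stratification as a clinical request. The entry for SAP amendment 3 says only that the SAP template was applied and endpoints were categorised.

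**The concern.** Someone programming from 14.2 would produce one column over all arms, split only by season. That column mixes people enrolled because they have COPD with people enrolled because they do not. A mean COPD-related cost or visit count from it is not a COPD figure. Within COPD it depends on how many of each GOLD grade the study chose to recruit, which is an operational decision.

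The larger loss needs no assumed rate. The clinical study report would hold no visit or cost result for COPD alone, none for any COPD group, and no contrast with the controls. The protocol's endpoint rationale table says these data are meant to support clinical management and public health resource allocation, and a pooled figure serves that poorly.

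**Working it through.** **1. Is pooling the natural reading?** The relevant parts of the SAP, side by side:

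- Section 2.2.2 names the breakdown for these data, and it is season.
- Section 5.4 sets out general summary statistics and no by-arm default.
- Sections 6.1, 6.3, 8.1, 8.2, 8.3, 9.2, 11, 12 and 15.1 ask for presentation by arm. Section 14.2 does not.
- Section 14.1, which covers treatment patterns (the other half of objective 3), lists GOLD grade as a subgroup.
- Nothing in Table 2 or 14.2 limits the analysis to COPD. In the schedule of activities, the utilisation and cost row does not carry the footnote that exempts healthy controls from other assessments.

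Pooling is therefore an inference from the wording and the silence. It is the likelier reading, but not an explicit statement.

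**2. Planned numbers** (protocol Synopsis). 1,700 + 180 + 120 = 2,000, and 700 + 700 + 200 + 100 = 1,700; both agree with the text. The documents state no visit rate or cost for this study that could be reproduced. The COPD mix is 700/1,700 = 41.2% each for GOLD I and II, 200/1,700 = 11.8% for GOLD III and 100/1,700 = 5.9% for GOLD IV.

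**3. Mean COPD-related visits or cost per participant.** Let c, b and h be the numbers with COPD, chronic bronchitis and healthy status. Let k be the chronic bronchitis mean as a fraction of the COPD mean, with healthy controls at zero. Then

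understatement = 1 − (c + k·b)/(c + b + h).

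| Case | Calculation | Understatement |
|---|---|---|
| Planned sizes, k = 0 | 1 − 1,700/2,000 | 15.0% |
| COPD −10%, others +10%, k = 0 | 1 − 1,530/1,860 | 17.7% |
| COPD +10%, others −10%, k = 0 | 1 − 1,870/2,140 | 12.6% |
| Planned sizes, k = 0.25 | 1 − 1,745/2,000 | 12.75% |
| Planned sizes, k = 0.5 | 1 − 1,790/2,000 | 10.5% |
| Planned sizes, k = 1 | 1 − 1,880/2,000 | 6.0% |

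**4. The crude rate.** Section 14.2 divides visits by the sum of (last visit date − first visit date + 1), and says that a visit in that chapter is a hospital attendance recorded in the database, not V1-V4. Read literally, a participant with no hospital record contributes no person-time, and one with a single record contributes one day. This shortens the denominator, which pushes the rate up, while pooling pushes it down.

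A simulation shows the range. It used 17,000 COPD and 3,000 non-COPD participants with Poisson visits over 2.5 years. The assumed rates were 0.5 to 4 COPD-related visits a year (COPD only) and 0.25 to 3 other visits a year (everyone). The pooled crude rate came out at 0.99 to 3.9 times the true COPD rate. With study time as denominator the same data gave about 0.85. The visit rates are assumptions, so the range shows only that the 0.85 factor cannot be carried over to this rate.

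**The case against.** **Silence is not pooling.** Overall and by season can be read as a contrast in time, the whole study against its seasons. SAP sections 7.2 (CID), 9.1 (CAT), 9.3 (EXACT), 9.4 (daily steps) and 10 (blood biomarkers) also leave out the by-arm wording, and nobody would expect those to be pooled. This stands in part: the text is ambiguous and pooling must be called an inference. But only for utilisation does the SAP name a different breakdown, and no default fills the gap.

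**The protocol does not require GOLD strata.** Section 5.4 speaks of groups of COPD patients without mentioning grade or severity, and 10.2.5 specifies no breakdown. The endpoint asks for overall and COPD-specific counts, and 14.2 separates COPD-related from other visits. That is correct, but separating visits by cause does not separate people by disease, and a table covering all arms cannot show any group of COPD patients.

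**There was a reason to change RAP 9.2.** Section 14.2 explains that scheduled-visit information is not in the hospital database, which accounts for dropping the summaries at visits 2, 3 and 4. It does not account for dropping arms, which are fixed at enrolment (SAP 5.2).

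**The size is conditional.** The 15% needs zeros entered for people with no COPD-related use, which 14.2 does not specify. It also needs the planned mix to survive the loss of five sites, whose composition is not given. This stands, so the figure is a ceiling on planned numbers.

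**Conclusion.** The point holds. Read as written, SAP 2.2.2 and 14.2 give no visit, rate or cost result for COPD, for groups within COPD, or against the controls. Objective 3 and protocol 5.4 call for the first two, and RAP 9.2 had a breakdown that supplied all three. It concerns the visit and cost tables only; treatment patterns are still reported by GOLD grade.

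For mean COPD-related visits or cost per participant, pooling would understate the COPD value by at most about 15% (12.6% to 17.7% across the size tolerance). This rests on the planned mix, zeros for non-users, and no COPD-related use outside COPD. If chronic bronchitis has the same rate as COPD, it is about 6%.

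A reader might infer three stronger things that the documents do not support:

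- *That the COPD visit rate will be up to 15% too low.* The crude rate does not use study time, so no direction is established for it.
- *That a severity gradient of known size is being hidden.* The documents give no visit rate or cost by GOLD grade.
- *That SAP 2.1 conceals a change.* Section 2.1 lists departures from the protocol, and protocol 10.2.5 set no breakdown to depart from. The unexplained loss is from the RAP, and belongs in the version history.

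**What to change.** In SAP 14.2 and 2.2.2:

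- Present every visit, rate and cost table by arm (GOLD I, II, III, IV, chronic bronchitis, healthy control) plus an all-COPD column made of the four GOLD arms, each with its own person-years.
- Take the COPD-related headline figures from the COPD columns, and label the all-COPD column as reflecting the recruitment targets.
- Base person-years on study follow-up, not on first to last hospital visit. SAP 6.1 already defines study duration from Visit 1 to the final visit.
- State whether participants with no COPD-related record count as zero.

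In the version history, record what changed from RAP 9.2 and why.

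The cost is extra columns in tables already planned, and a denominator taken from a duration already derived. No new data are needed, provided that hospital records can be linked to the study identifier.
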